## PROTOCOL SUMMARY

Title	Retrospective evaluation of treatment durability among treatment-naive HIV-infected individuals initiated first-line ART in Russia
Supplier	Atlant Clinical Ltd
Rationale	Treatment durability is an important factor in HIV disease management since HIV infected individuals need to take ART life-long. To date, there is limited data on treatment durability in HIV infected individuals initiating ART in Russia. Understanding the durability of treatment is essential for improving medical care of patient living with HIV.
Primary Objective	To evaluate the 48 weeks treatment durability among treatment naive HIV-infected individuals determined as a percentage of patients remained on initial therapy
Study Design	A non-interventional retrospective study.
Study Population	Treatment-naive at the time of initiation of ART with NNRTI plus two NRTIs or PI boosted by ritonavir with 2 NRTIs per usual standard of care of the investigator in AIDS clinics of Russia.
Study Duration	Up to 24 months will be dedicated to retrospective data collection and analysis from treatment-naïve HIV-infected patients who initiated their first-line ART between February 01 and June 30, 2017
Exposure and Outcome	Initial ART per usual standard of care in AIDS clinics of Russia: NNRTI plus 2 NRTIs or PI boosted by ritonavir with 2 NRTIs. Treatment durability determined as a percentage of patients continuing their first-line for 48 and 96 weeks without changes (switch or withdrawal) evaluated retrospectively
Statistical Methods	Data will be presented descriptively as follows: the number of observations, mean and standard deviation, median, first and third quartiles, minimum and maximum for continuous variables, and the absolute frequencies and percentage of patients presenting the given feature for qualitative variables. The results on the study endpoints (proportion of patients who remain on first-line ART at 48 and 96 weeks) will be presented with two-sided 95% confidence intervals. Univariate and multivariate logistic regression will be used to study the association between patients' baseline demographic and clinical characteristics and treatment discontinuation status.

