## 1 Background and Rationale

### 1.1 Background

Human immunodeficiency virus infection and acquired immune deficiency syndrome (HIV/AIDS) is a spectrum of conditions which interfere with increasing the risk of developing common infections such as tuberculosis, as well as other opportunistic infections, and tumors that rarely affect people who have working immune systems.[1] These late symptoms of infection are referred to as acquired immunodeficiency syndrome (AIDS).[2] From the time AIDS was identified in the early 1980s to 2017, the disease has caused an estimated 35 million deaths worldwide.[3] In 2016, about 36.7 million people were living with HIV and it resulted in 1 million deaths.[4] Unlike most countries, Russia's HIV epidemic is growing, with the rate of new infections rising by between 10 and 15% each year. It is estimated that over 250 people become infected with HIV every day. [5, 6] By mid-2017, 1.16 million people had been diagnosed with HIV in Russia. However, this does not equate to the number of people currently living with HIV as it does not account for AIDS-related deaths or people who have HIV but are undiagnosed. Although Russia has collected extensive data on HIV since 1987, official estimates for these measures remain under reported and inconsistent. A 2017 data analysis suggests the numbers of AIDS-related deaths are rising. From January to June 2017, 14,630 AIDS-related deaths were recorded, a 13.5% increase over the previous six-month period. HIV is one of the top 10 causes of premature death in Russia. [7, 8]

Life expectancy of people living with HIV (PLWH) increased substantially with the introduction of combined active antiretroviral therapy (cART) [9]. Consequently, assessing long-term treatment outcomes and regimen durability has become increasingly relevant. Patients still experience treatment modifications and interruptions for reasons that may include virological failure, adverse events, or poor adherence [10, 11]; and treatment modifications or interruptions may be associated with increased costs or adverse clinical outcomes. Efavirenz (EFV) and other NNRTIs are the preferred options for the third component in first antiretroviral regimens (first-line ART) to treat HIV infection, according to the World Health Organization Consolidated Guidelines (WHO) [12] and Russian National cART guidelines [13].

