Baseline and follow-up data will be extracted through retrospective chart or medical records review, if available at each investigational site. No additional interventional tests or medical procedures such as additional blood samples, X-ray or other technical investigations will be performed as a part of this study. If any data element is not available, it will be reported as missing.

At baseline, demographic and clinical data on age, gender, employment status, marital status, substance abuse, HIV diagnosis duration, route of infection, AIDS stage, viral load, CD4 count, concomitant medication, comorbidities (noted diagnosis by physician) are to be collected through retrospective chart or medical records review.

At 48 and 96 weeks of retrospective follow-up, the investigators will assess through the medical records whether the patient was still on treatment with initiated ART (NNRTI, PI) and evaluate the estimated time on therapy without change of the NNRTI or PI agent within the class or without change of the NNRTI or PI agent to a different class.

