### 4.3 Outcomes

#### 4.3.1. Treatment Durability

Treatment durability is determined as a percentage of patients continuing their first-line ART with NNRTI plus 2 NRTIs or PI boosted by ritonavir with 2 NRTIs for 48 and 96 weeks without change of the NNRTI or PI agent (“anchor” or “third agent”) within the class or without change of the NNRTI or PI agent to a different class.

According to the Primary objective, the treatment durability is to be retrospectively evaluated at 48 weeks from the time of initiation.

According to the Exploratory objective, the treatment durability is to be retrospectively evaluated at 96 weeks from the time of initiation.

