#### 4.3.1. Time on therapy

According to the Secondary objective, the estimated time on therapy (weeks) without change of the NNRTI or PI agent (“anchor” or “third agent”) is to be retrospectively evaluated at week 48 from the time initiation.

According to the Exploratory objective, the estimated time on therapy (weeks) without change of the NNRTI or PI agent (“anchor” or “third agent”) is to be retrospectively evaluated at week 48 from the time initiation.

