## Study Flow Chart

## Study Procedures

Study period	Screening	Retrospective clinical data extraction through chart or medical records review
Visit Number	0	1
Screening and chart review	X	
Informed consent	X	
Inclusion/Exclusion criteria	X	
Age at baseline		X
Gender at baseline		X
Employment status at baseline		X
Marital status at baseline		X
Substance abuse		X
HIV diagnosis duration at baseline		X
Route of infection at baseline		X
HIV stage at baseline		X
Viral load at baseline		X
CD4 at baseline		X
Concomitant medications at baseline		X
Comorbidities at baseline		X
Initial ART at baseline		X
Treatment durability: NNRTI or PI continuation at Week 48/96		X
Estimated time on treatment with NNRTI or PI at Week 48/96		X
Adverse events at baseline and at Week 48/96		X

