#### **7.1.1 Primary Objective:**

- Percentage of HIV-infected patients remained on first-line ART at 48 weeks after the start of treatment will be presented descriptively with 95% confidence interval by initial ART regimen (NNRTI or boosted PI plus 2 NRTIs) and overall

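### The primary outcome is defined inconsistently for treatment interruption: a patient who stops ART and restarts the same agent can be scored either way

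*Combined protocol and SAP*

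**What the plan says.** The outcome appears in three forms.

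- **Switch or withdrawal over the period.** The Protocol Summary (Exposure and Outcome) defines durability as the percentage of patients "continuing their first-line for 48 and 96 weeks without changes (switch or withdrawal) evaluated retrospectively".
- **Change of the third agent.** Section 2.1, the secondary objectives in 2.2, both subsections numbered 4.3.1 and the Kaplan-Meier bullets of 7.1.2 describe the event as a change of the NNRTI or PI agent. Section 4.3.1 (Treatment Durability) asks for continuation "for 48 and 96 weeks without change of the NNRTI or PI agent". Section 4.3.1 (Time on therapy) asks for weeks "without change of the NNRTI or PI agent". Withdrawal is not mentioned in these places.
- **Status at the time point.** Section 3.1 says that at 48 and 96 weeks "the investigators will assess through the medical records whether the patient was still on treatment with initiated ART", and adds an estimate of time on therapy without change of agent. The Study Procedures table lists "Treatment durability: NNRTI or PI continuation at Week 48/96" and a second row for estimated time on treatment. Section 7.1.1 analyses the "Percentage of HIV-infected patients remained on first-line ART at 48 weeks after the start of treatment".

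The regression in 7.1.2 models discontinuation of initial ART, which is not defined. Section 1.1 recognises that gaps in therapy occur: "Patients still experience treatment modifications and interruptions for reasons that may include virological failure, adverse events, or poor adherence". No section says what length of gap is tolerated or how a stop followed by restart of the same agent is scored. The listed data items include no stop or restart date.

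**The concern.** Stopping all ART and later restarting the same agent is a withdrawal under one definition, a non-event under the second, and visible under the third only if the patient happens to be off drug at week 48 or 96. Up to 8 sites would each have to choose a reading while extracting charts. Without stop and restart dates, the central analysis could neither detect nor correct differences between sites.

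This affects the primary percentage, the 96-week percentage, the Kaplan-Meier time and the regression outcome, because all four depend on what ends initial therapy. Two features of the design make it more than a drafting matter:

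- The visit window of about ±8 weeks in Section 3.1 gives extra room for a restart near a time point to be recorded as being on treatment.
- Section 3.3 requires at least 96 weeks of completed follow-up and signed consent. Patients who stopped and left care are therefore unlikely to be enrolled, and interrupters in this cohort plausibly include many who came back.

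**Working it through.** **1. The plan's own precision figure.** Section 7.3 gives an assumed proportion p = 0.70, n = 1000 and a 95% Wald interval.

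Half-width = 1.96 × √(0.70 × 0.30 / 1000) = 0.0284, so the interval is 67.2% to 72.8% and the width 5.7 points. This matches the plan, and the other five rows of the table also reproduce to rounding. The precision calculation is not in dispute.

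**2. Two patients under the three definitions.**

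- Patient A starts efavirenz, stops all ART at week 10, restarts efavirenz at week 40 and is on it at week 48.
- Patient B is off therapy at week 48, has restarted the same agent by week 96 and is on it then.

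| Definition | A at week 48 | A: time at week 48 | B at week 48 | B at week 96 |
|---|---|---|---|---|
| Switch or withdrawal (Protocol Summary) | fails | 10 weeks, to first stop | fails | fails |
| Change of agent only (2.1, 4.3.1, Kaplan-Meier text of 7.1.2, read literally) | durable | 48 weeks, agent never changed | durable | durable |
| Status at the time point (3.1, Study Procedures, 7.1.1) | durable | 10 + (48 − 40) = 18 weeks on treatment | fails | durable |

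The 18-week figure comes from the row for estimated time on treatment in the Study Procedures table, read as weeks actually on drug. The 30 weeks between stop and restart separate it from 48.

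**3. Consequences.**

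- On the status reading, patient B fails at 48 weeks and passes at 96. The two percentages are then not nested, so the 96-week figure is not limited to patients who passed at 48 weeks.
- A Kaplan-Meier curve cannot rise, so it cannot reproduce B's pattern.
- If the curve's event is a change of agent, B is event-free at week 48 on the curve but a failure in the 7.1.1 percentage. If the event includes withdrawal, A is an event at week 10 on the curve but durable in the percentage. Either way the two results can disagree.

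**4. Scale.** Let f be the share of patients on the initial agent at week 48 who had earlier stopped and restarted it. Take 70% as the on-agent percentage. The uninterrupted-use percentage is then 70% × (1 − f). The documents give no value for f, so these values are assumptions:

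| f | Uninterrupted-use percentage (95% Wald CI, n = 1000) | Shift |
|---|---|---|
| 1% | 69.3% (66.4 to 72.2) | 0.7 points |
| 2% | 68.6% (65.7 to 71.5) | 1.4 points |
| 4% | 67.2% (64.3 to 70.1) | 2.8 points |
| 5% | 66.5% (63.6 to 69.4) | 3.5 points |
| 10% | 63.0% (60.0 to 66.0) | 7.0 points |

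The shift equals the planned half-width at f = 0.0284 / 0.70 = 4.1%, that is 0.0284 × 1000, or about 28 patients.

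**The case against.** The strongest defence is that the plan already contains a strict definition. Section 4.3.1 speaks of continuing for 48 and 96 weeks, and the Protocol Summary treats withdrawal as a change. On that text, a patient who stops all ART at week 10 has not continued and fails. The data collection is not a bare yes/no check either, since the Study Procedures table also asks for estimated time on treatment. Section 5.3 says the eCRF is still to be developed, so date fields may yet appear. An outcome based only on change of the third agent would also be a legitimate choice: Section 1.2 gives the probability of needing a switch as a reason for the study.

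These points rule out several stronger readings that a reader might infer:

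- **That patients who stop and restart are counted as durable for the full period.** No section says so, and the period wording supports the opposite.
- **That interruption always inflates durability, or does so by some stated number of points.** The upward error arises only where the status or change-of-agent reading is applied and uninterrupted use is the target. The documents supply no interruption rate.
- **That associations with, for example, substance abuse or employment are weakened.** This would need stop-and-restart to differ between those groups, and the documents give no such data.

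The defence does not remove the inconsistency. Withdrawal appears as a failure only in the Protocol Summary and is never defined. The time-on-treatment row does not say whether a gap is subtracted, ends the count or is ignored. The strict reading cannot be applied uniformly from the items listed.

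**Conclusion.** The point holds as an inconsistent outcome definition, not as a demonstrated bias. As written, the same patient can be scored durable or not, can be given 48, 18 or 10 weeks on therapy, and can make the percentages and the Kaplan-Meier curve disagree. The size is unknown. The figure of about 28 patients in 1000 is a yardstick that rests on the plan's 70% and n = 1000; it does not estimate how many such patients there will be. The point should be settled before extraction, because differences between sites could not be repaired afterwards without going back to the charts.

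**What to change.** - **Definition.** Reconcile the Protocol Summary, Sections 3.1 and 4.3.1 (both parts), the Study Procedures table and Sections 7.1.1 and 7.1.2. Use one event, switch or withdrawal of the third agent as in the Protocol Summary, for the percentage, the Kaplan-Meier time and the regression. State explicitly how a stop followed by restart of the same agent is classified.
- **Data.** Add to the data collection the date the third agent was first stopped or changed, and any restart date.
- **Gap rule.** Prespecify the minimum gap that counts as a stop before extraction begins. Its length is for the sponsor to choose.
- **Reporting.** Report both the uninterrupted-use percentage and the percentage on the initial agent at weeks 48 and 96, with one named in advance as the sensitivity analysis.

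The cost is some rewording and a few eCRF fields, filled from charts already being read. The main durability figure may come out lower. Short gaps may be incompletely charted, which is a reason to fix a minimum gap rather than leave the outcome open.

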### **3.2 Study Population**

All patients enrolled must be treatment naive at the time of initiation of ART with NNRTI plus two NRTIs or PI boosted by ritonavir with 2 NRTIs per the usual standard of care of the investigator in AIDS clinics of Russia.

### **3.3 Inclusion Criteria**

- Adult patients (>18 years of age) with definite HIV-1 infection based on positive lab test and judgement of treating physician according to standards of care
- Naive to antiretroviral treatment at the time of initiation
- Viral load of >1000 copies/ml at the time of initiation of ART
- Initiated their first-line ART between February 01 and June 30, 2017
- Patients are included, if the third component of their first line ART was either NNRTI or boosted PI plus 2 NRTIs
- Completed follow-up from baseline for at least 96 weeks
- Signed informed consent

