## 2 Objectives and Hypotheses

### 2.1 Primary Objective

- To evaluate the 48 weeks treatment durability among treatment naive HIV-infected individuals initiated ART (NNRTI, PI) determined as a percentage of patients remained on initial therapy without change of the NNRTI or PI agent

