## 3 METHODOLOGY

### 3.1 Summary of Study Design

This study is a non-interventional retrospective study. Data from patients who signed informed consent form will be collected through retrospective chart or medical records review. Patients have been receiving treatment and diagnostic procedures according to daily clinical practice conducted by his/her physician. There are no procedures that are required as part of this study.

The study is to be conducted in up to 8 investigational sites across Russia with up to 200 patients recruited per site. Each investigational site will be a dedicated HIV clinic or an HIV department in clinic of infectious diseases. It is planned that the first half of the study population (500 patients) will be enrolled during the first 6-9 months and the second half of the study population (500 patients) during the second 6-9 months of the study.

HIV-infected patients with no experience of therapy at time of initiation of ART with NNRTI plus two NRTIs or PI boosted by ritonavir with 2 NRTIs will be enrolled and followed retrospectively for up to 96 weeks with data collection at the approximate time points of baseline (pre-treatment) and at 48 and 96 weeks after start of treatment.

The following ARV drugs are considered according to the standards of care:

- NNRTIs: efavirenz (EFV), nevirapine (NVP), rilpivirine (RPV), ETR (etravirine) etc.
- PIs: LPV (lopinavir), DRV (darunavir), ATV (atazanavir), FPV (fosamprenavir) etc.

All patients must have initiated ART between February 01 and June 30, 2017. A time window for the retrospective visits at baseline, 48 and 96 weeks is envisaged as approximately  $\pm$  8 weeks.

Patients will be retrospectively screened and selected according to inclusion and exclusion criteria prior to enrollment in each investigational site starting the day of its initiation. The study sites will maintain a list of all screened patients. All patients eligible according to the inclusion/exclusion criteria and after signing the informed consent form are to be consequently enrolled for their demographic and clinical data collection through retrospective chart or medical records review. The enrollment will continue until the recruitment goal is reached.

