## **5.1 General Informed Consent**

Consent must be documented by the subject's dated signature or by the subject's legally acceptable representative's dated signature on a consent form along with the dated signature of the person conducting the consent discussion.

A copy of the signed and dated consent form should be given to the subject before the demographic and clinical data are extracted through retrospective chart or medical records review.

The initial informed consent form, any subsequent revised written informed consent form and any written information provided to the subject must receive the IRB/ERC's approval/favorable opinion in advance of use. The informed consent will adhere to IRB/ERC requirements, applicable laws and regulations and Sponsor requirements.

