#### **7.1.2 Secondary Objectives:**

- Time on therapy (weeks) without change of the NNRTI or PI agent at week 48 from the ART initiation will be presented in Kaplan-Meier plots
- Demographic and clinical characteristics at baseline will be presented descriptively by initial ART regimen (NNRTI or boosted PI plus 2 NRTIs) and overall
- Association between characteristics of patients and treatment durability at 48 weeks will be investigated via:
  - Subgroup analysis: number and percent of patients continuing treatment at 48 weeks will be presented descriptively by demographic and clinical characteristics categorized according to 8.1.4
  - Multivariate logistic regression analysis to identify potential risk factors for discontinuation of initial ART at 48 weeks. Demographic and clinical characteristics categorized according to 8.1.4 will be included into multivariate analysis only if they are found significant in univariate logistic regression analysis. Unadjusted (univariate model) and adjusted (multivariate model) odds ratios will be presented with 95% confidence intervals for the parameters included in each of the analyses.
- Percentage of HIV-infected patients remained on first-line ART at 96 weeks after the start of treatment will be presented descriptively with 95% confidence interval by initial ART regimen (NNRTI or boosted PI plus 2 NRTIs) and overall
- Time on therapy (weeks) without change of the NNRTI or PI agent at week 96 from the ART initiation will be presented in Kaplan-Meier plots
- Association between characteristics of patients and treatment durability at 96 weeks will be investigated via:
  - Subgroup analysis: number and percent of patients continuing treatment at 96 weeks will be presented by demographic and clinical characteristics categorized according to 8.1.4

- Multivariate logistic regression analysis to identify potential risk factors for discontinuation of initial ART at 96 weeks. Demographic and clinical characteristics categorized according to 8.1.3 will be included into multivariate analysis only if they are found significant in univariate logistic regression analysis ( $p<0.1$ ). Unadjusted (univariate model) and adjusted (multivariate model) odds ratios will be presented with 95% confidence intervals for the parameters included in each of the analyses.

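### Entry requires 96 weeks of completed follow-up and signed consent, so as worded the durability figures describe retained, consenting patients rather than the ART initiators named in section 2.1

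*Combined protocol and SAP*

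**What the plan says.** The primary objective (section 2.1) is to evaluate the "48 weeks treatment durability among treatment naive HIV-infected individuals initiated ART (NNRTI, PI"), with no condition on what happens to them later. Section 3.3 adds two entry conditions beyond the clinical ones: "Completed follow-up from baseline for at least 96 weeks", and signed informed consent. Section 5.1 lets the patient or a legally acceptable representative sign, and requires that a copy of the form be given "before the demographic and clinical data are extracted through retrospective chart or medical records review". Section 3.1 limits data collection to patients who signed.

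The Protocol Summary defines durability as continuing first-line therapy "without changes (switch or withdrawal"). On gaps in the records, section 3.1 states: "If any data element is not available, it will be reported as missing". Neither place says how death or loss to care is counted.

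Sections 7.1.1 and 7.1.2 plan percentages at weeks 48 and 96, logistic models, and time on therapy, which "at week 48 from the ART initiation will be presented in Kaplan-Meier plots", and likewise at week 96. No other analysis population, weighting or sensitivity analysis is defined. Section 7.2 names recruitment errors as the source of bias, and 7.2.1 offers strict adherence to the entry criteria as the remedy. Section 7.2.3 adds missing data and undetected earlier ART. Section 3.1 also provides: "The study sites will maintain a list of all screened patients". No reporting of that list is planned.

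**The concern.** Entry to a week-48 percentage depends on events up to week 96, twice the primary horizon, and on consent obtained later still. The patients removed this way are not a random sample of initiators. Some had stopped the initial agent by week 48. Others were still taking it and left care afterwards. The percentages, Kaplan-Meier curves and odds ratios all inherit the selection. Following the 7.2.1 remedy enforces it.

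The sample size is justified only by the precision of the week-48 proportion. That interval covers sampling error in the enrolled cohort. If the result is reported as durability among initiators, the interval says nothing about the difference between the two populations, and enrolling more patients does not reduce that difference.

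**Working it through.** **1. The plan's own figure.** Inputs from section 7.3: assumed proportion 0.70, n = 1000, 95% Wald interval. Half-width = 1.96 × √(0.70 × 0.30 / 1000) = 0.0284. The interval is 67.16% to 72.84%, width 5.68 points. This matches the stated 67.2% to 72.8%, 5.7% (±2.8%).

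**2. Timing.** Initiation ran from 1 February to 30 June 2017 (section 3.3). Adding 96 weeks (672 days) puts week 96 between 5 December 2018 and 3 May 2019. A patient who died or left care before then has not completed 96 weeks of follow-up, whatever their status at week 48. Section 3.1 allows about ±8 weeks around each time point, so the boundary is approximate. Patients who switched the third agent but stayed in care remain eligible and count as not durable.

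**3. Effect on the percentage.** The documents do not give the next two quantities, so both are assumptions:
- e, the share of otherwise eligible initiators who are excluded;
- q, the share of those excluded who were still on the initial agent at week 48.

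With true durability 0.70 among all initiators, the cohort shows (0.70 − e·q)/(1 − e), and the bias is e(0.70 − q)/(1 − e).

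| e | q = 50% | q = 80% |
|---|---|---|
| 5% | 0.675/0.95 = 71.1% | 0.66/0.95 = 69.5% |
| 10% | 0.65/0.90 = 72.2% | 0.62/0.90 = 68.9% |
| 20% | 0.60/0.80 = 75.0% | 0.54/0.80 = 67.5% |

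The cohort figure is too high if q is below 70%, unbiased at 70%, and too low above it.

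**4. When the bias exceeds the stated half-width.** Setting the bias equal to ±0.0284 gives q = 0.70 ∓ 0.0284(1 − e)/e.
- e = 5%: 0.0284 × 19 = 0.540, so only if q is below 16%. No q above 70% is large enough.
- e = 10%: 0.0284 × 9 = 0.256, so if q is below 44% or above 96%.
- e = 20%: 0.0284 × 4 = 0.114, so if q is below 59% or above 81%.

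**5. Bounds without assuming q.** If the cohort shows p, the value among all initiators lies between p(1 − e), with all excluded patients off therapy, and p(1 − e) + e, with all on. For p = 70% this is 63.0% to 73.0% at e = 10% and 56.0% to 76.0% at e = 20%. The width is e, so above e = 5.7% the bounds are wider than the stated interval.

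**The case against.** The strongest reply is that the criterion may mean only that 96 weeks have elapsed since initiation. The Kaplan-Meier plots, the separate column for known status in the 7.3 table and the provisions for missing data are all compatible with that. The criterion says completed follow-up, which points the other way, but the retention part of this point does depend on the wording. The consent part does not: on either reading, data come only from patients who signed or were represented at enrolment.

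It can also be said that the study is descriptive, tests no hypothesis, and could keep its criterion if the target were restated. That is fair, and it is why restatement is offered below as a sufficient alternative.

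Several stronger inferences are tempting, and the documents do not support them.
- *Sections 3.1 and 3.3 contradict each other.* Section 3.1 says patients are "enrolled and followed retrospectively for up to 96 weeks". That is the horizon for data collection, while 3.3 sets a minimum for eligibility. A patient with 120 weeks of records satisfies both.
- *Section 7.2.3 explains the 96-week criterion.* It says only that a set of core variables must be available at enrolment. No section gives a reason for the 96 weeks.
- *Durability must be overestimated.* Patients lost between weeks 48 and 96 may have been on the initial agent at week 48, so q could exceed 70%.
- *Consent excludes everyone who died or cannot sign.* Section 5.1 allows a representative to sign.
- *The plan keeps no trace of those left out.* Section 3.1 requires a screening list. What is missing is a record of reasons and any reporting of it.

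**Conclusion.** The point holds. As worded, sections 2.1 and 3.3 describe different populations. No planned analysis bridges them, and sections 7.2 to 7.2.3 do not name the gap. If elapsed time was intended, the retention part is settled by saying so, and the consent selection remains.

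Direction and size cannot be read from the documents. The figures above rest on assumed values of e and q and on the plan's 70%, and they show only what could happen. With 5% excluded, the bias is within the stated 2.84 points for most values of q. With 20% excluded, it is within that margin only if q lies between about 59% and 81%. They do not show that the bias in this study is large.

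**What to change.** **Option A: keep the target in 2.1.**
1. Replace the follow-up criterion with: *ART initiated at least 96 weeks before data extraction, whether or not follow-up continued*.
2. Count documented stopping of the initial agent before the time point as not remaining on initial therapy.
3. State how death before the time point is handled. I propose counting it as not remaining, with a sensitivity analysis, because the Protocol Summary names only switch or withdrawal. The choice is the sponsor's.
4. Report loss to care before the time point in two ways: as not remaining, and as censored at last contact in a Kaplan-Meier estimate. A patient documented on the agent at week 48 and lost later counts as remaining at week 48.
5. Censor transfers of unknown status at transfer in the Kaplan-Meier estimate, and give bounds with all of them off and all on therapy.
6. Ask the ethics committee whether chart data of deceased or untraceable patients may be used.
7. If consent stays an entry condition, this option does not by itself reach all initiators. State that the estimate applies to consenting patients and, if the committee allows, report counts and bounds for those not enrolled.

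**Option B: keep the criterion.** Restate the target in 2.1 and in all conclusions as patients retained for 96 weeks who consented. If the ethics committee allows, use the screening list to tabulate otherwise eligible initiators not enrolled, by reason, with all-off and all-on bounds.

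Under either option, name retention and consent selection as a bias in 7.2.

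**Cost.** Both options need an ethics query, and neither adds patient procedures. Option A brings some incomplete records, possibly a different headline percentage, and slightly wider intervals. If 10% of 1000 have unknown status, the half-width is 1.96 × √(0.21/900) = 2.99 points; at 20% it is 1.96 × √(0.21/800) = 3.18 points, against 2.84. Option B needs fuller screening lists at up to 8 sites, and its bounds are uninformative if many patients are not enrolled, since their width equals the excluded share.
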